#### Furthermore:

- Survival information, Adverse Drug Reaction (ADR) and Adverse Events of Special Interest (AESI) will continue to be collected for any single patient until end of study visit, consent withdrawal, lost to follow up or death
- If the patient withdraws consent for disclosure of future information, the Sponsor may retain and continue to use any data collected before such a withdrawal of consent
- If a patient withdraws from the study, he/she may request destruction of any samples taken and not tested, and the Investigator must document this in the study site records
- The Investigator and Sponsor may continue to use publicly available information to establish the survival status of patients who have withdrawn consent

See Schedule of activities (Section 1.2) for data to be collected at the time of treatment discontinuation and follow-up and for any further evaluations that need to be completed.

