### Reasons for this Amendment

The primary reasons for this amendment are:

- 1. To update the design and size of the study to remove the study expansion phase, due to difficulties in recruitment in the study.
- 2. To restrict individual patient's follow-up to a maximum of 25 months (including clarification of reasons for earlier withdrawal), which is the follow-up required for the study primary endpoint. A longer follow up was envisaged for efficacy assessment but has a limited value considering the reduced sample size.
- 3. To update the study objectives to formally list the biodistribution of Betalutin in combination with rituximab (RTX) and to establish a recommended dose of Betalutin in combination with RTX for phase 2 studies as objectives and to describe the endpoints for pharmacokinetics, pharmacodynamics and biodistribution studies. This is to rectify an oversight in the initial protocol.

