#### **Secondary**

- Responses (overall response rate [ORR], CR, PR, stable disease [SD], progressive disease [PD]) as per Cheson 2014
- Duration of response (DoR)
- Progression free survival (PFS)
- Time to progression (TTP)
- Overall survival (OS)
- Monitoring of the anti-drug antibody (ADA) response towards lilotomab, Betalutin and/or RTX

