# 4.5. End of Study Definition

The end of study for all patients will be the date of the last patient last visit upon completion of their end of study visit(25 months after receiving their Betalutin treatment if ending study treatment per protocol, or after disease progression or withdrawal from the study for any other reason, (whichever comes first) or if the study is terminated early.

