## 7.2. Patient Withdrawal/Discontinuation from the Study

In accordance with the Declaration of Helsinki, each patient is free to withdraw from the study at any time. Investigator(s) also have the right to withdraw patients from the study in the event of illness, AEs, or other reasons concerning the health or well-being of the patient, or in the case of lack of cooperation.

Should a patient decide to withdraw after administration of the study drug(s) or should the Investigator(s) decide to withdraw the patient, all efforts will be made to complete and report the observations up to the time of withdrawal as thoroughly as possible. A complete final evaluation at the time of the patient's withdrawal (end of study visit) should be made within 28 days (± 3 days) of receiving the last study treatment administration if ending treatment per protocol, or within 7 days of taking the decision to withdraw if it occurs > 28 days after the last study treatment administration and an explanation given of why the patient is withdrawing or being withdrawn from the study. The reason and date for withdrawal must be noted in the eCRF. If the reason for withdrawal is a clinical AE or an abnormal laboratory test result, monitoring will continue until the outcome is evident. The specific event or test result(s) must be recorded in the eCRF. If the reason for withdrawal is due to disease progression, the study site should make all effort to continue with the safety monitoring.

Haematological toxicity was observed in the phase 1/2 LYMRIT-37-01 study, with nadir values 5 to 7 weeks after injection of Betalutin. It is advisable to monitor the haematology parameters of the withdrawn patients between 6 and 9 weeks after the last RTX administration or until recovery to CTCAE grade 1 or less.

Single patient study discontinuation is per definition, when the patient:

- has completed Month 24 administration of rituximab, per protocol or
- experiences one of the following situations before per protocol end of study:
  - withdraws consent to participate in the study
  - has died
  - is lost to follow up
  - has disease progression
  - starts further anticancer therapy or
- when the patient is withdrawn for a reason other than described above

CONFIDENTIAL

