#### **8.2.19.** End of study visit – Hospital Visit

The end of study visit should occur:

- 28 days (± 3 days) post last rituximab administration for patients, who complete the study per protocol (Month 25/Week 108)
- Within 7 days of decision of withdrawing from the study is made if the decision occurs > 28 days post last administration of study treatment for patients who discontinue from the study before Month 24 (e.g. disease progression, start of new anti-cancer therapy, other reason) An end of study visit is not expected for patients, who discontinue due to death, lost to follow up or withdrawal of consent.

Safety follow-up procedures 4 weeks after administration of the final RTX study dose are outlined in Table 8-22.

Patients in survival follow-up at the time of Protocol v4.0 approval can have the EOS visit at their next scheduled visit or an earlier convenient time point

Table 8-22 Procedures and assessments at end of study visit

Assessment or Procedure	Explanation	
Concomitant medication	Recording of concomitant medication used since the previous visit	
Physical examination	Any abnormal findings will be recorded in the AE record	
Vital signs	Systolic/diastolic blood pressure, heart rate and body temperature	
ECOG	ECOG performance status	
Haematology	Including haemoglobin, platelet count, white blood cell count and differential (absolute count of neutrophils, lymphocytes, monocytes, eosinophils and basophils)	
Serum biochemistry	Including sodium, potassium, calcium, magnesium, creatinine, urea, uric acid, ALP, ASAT, ALAT, LDH, GGT, glucose, total bilirubin and albumin	
Adverse events	Any AEs / AESIs occurring since prior visit will be recorded	

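### Section 7.2 ends survival collection at an end of study visit that progression triggers, other current text implies it continues, and OS is kept as a secondary endpoint with no stated censoring rule

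*Combined protocol and SAP*

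**What the plan says.** All references are to the combined protocol and SAP, v4.0.

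**Text that ends collection**
- Section 7.2 begins its list with "Single patient study discontinuation is per definition, when the patient" and includes disease progression and the start of further anticancer therapy.
- Section 4.5 places a patient's end of study visit at 25 months after Betalutin, "or after disease progression or withdrawal from the study for any other reason, (whichever comes first".
- Section 8.2.19 sets an early visit "for patients who discontinue from the study before Month 24 (e.g. disease progression, start of new anti-cancer therapy, other reason", normally within 7 days of the decision.
- Section 7.2 then says that survival information, ADRs and AESIs "will continue to be collected for any single patient until end of study visit, consent withdrawal, lost to follow up or death".

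**Text that points to continued collection**
- Tables 1-1 and 1-2 keep a survival-status row that cites 7.2.
- Footnote 24 provides for a six-monthly check at a visit or by telephone. The neighbouring footnote 23 is marked as removed in v4.0; footnote 24 is not.
- Section 9.2.4 sends deaths more than 12 weeks after the last study drug to the eCRF as survival information, with no end date.

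**Transition.** Section 8.2.19 adds: "Patients in survival follow-up at the time of Protocol v4.0 approval can have the EOS visit at their next scheduled visit", or earlier if convenient.

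**Analysis.** OS is a secondary endpoint in the synopsis and Table 3-1, and 10.1 lists it among the efficacy measures to be summarised. No time origin, estimator or censoring rule for OS is given. The one rule for withdrawn patients in 10.1 counts them as PD at later visits.

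**The concern.** Censoring is harmless for a survival curve only if patients who leave have the same prospects as those who stay. Progression breaks that condition: section 2.2.1 itself cites 5-year OS of 50% after early progression against about 90% for all FL. If collection stops at a visit that progression triggers, later deaths are not recorded, and the curve moves towards the survival of patients who have not progressed.

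Two features add to this. Patients who progressed before v4.0 and were already in survival follow-up contributed time after progression, whereas those who progress under v4.0 do not, so one OS summary would combine two follow-up rules. And the gap cannot be closed at analysis: a later SAP could supply a censoring rule, but it could not recover deaths that were never collected.

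At stake is the meaning of one descriptive endpoint.

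**Working it through.** **1. The plan's own figures.** Two cohorts of 3 to 6 give 2 × 3 = 6 and 2 × 6 = 12, the stated sample size. Week 104 + 4 weeks = Week 108, and 108 × 7 / 30.4375 = 24.8 months, which agrees with Month 25. The plan gives no OS assumption to reproduce.

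**2. Inputs**
- First patient October 2018; expected accrual 18 months (synopsis, Key dates). v4.0 is dated 04 October 2021, that is 36 months after the start. The approval date and actual accrual are not given.
- Assumed death hazard per month before progression: h0 = −ln(0.90)/60 = 0.00176. After progression: h1 = −ln(0.50)/60 = 0.01155, or −ln(0.58)/60 = 0.00908. These borrow the 5-year OS figures in 2.2.1 for all FL, early progression and rituximab-refractory disease.
- Assumed median time to progression m = 9, 12 or 18 months, hp = ln2/m. Section 2.4 offers anchors: 7–10 months on rituximab alone, and a median response of over 12 months with Betalutin.

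**3. Model.** At patient time s:
- alive without progression: P0 = exp(−(hp+h0)s)
- alive after progression: P1 = hp[exp(−h1·s) − exp(−(hp+h0)s)]/(hp+h0−h1)
- true OS = P0 + P1

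**4. A patient wholly under v4.0.** Censored at progression, Kaplan-Meier targets exp(−h0·t). At t = 25 this is exp(−0.00176 × 25) = 95.7%. With m = 12 and h1 from 50%, true OS = 0.226 + 0.630 = 85.6%, a difference of 10.1 points. Over all six combinations:

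| m (months) | h1 from 50% | h1 from 58% |
|---|---|---|
| 9 | 11.9 | 9.1 |
| 12 | 10.1 | 7.7 |
| 18 | 7.7 | 5.9 |

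If mortality after progression were no higher than before it, the bias would be zero.

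**5. The trial's calendar.** Let entry be uniform over A months and v4.0 take effect at month V. A progressed patient is still followed at time s with probability q(s) = min(1, (V−s)/A). The observed hazard is (h0·P0 + h1·P1·q)/(P0 + P1·q). Bias at 24 months is exp(−integral of that hazard from 0 to 24) minus true OS. Patients in survival follow-up are assumed to leave at V, the earliest exit that 8.2.19 allows. Bias in percentage points over the six combinations:

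| Accrual A (months) | V = 36 | V = 39 | V = 42 |
|---|---|---|---|
| 18 | 0.12–0.25 | 0.03–0.06 | 0 |
| 24 | 0.46–0.79 | 0.23–0.42 | 0.09–0.18 |
| 30 | 0.96–1.46 | 0.60–0.98 | 0.34–0.60 |
| 36 | 1.53–2.19 | 1.09–1.61 | 0.74–1.16 |

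At V = 36, deaths not collected by Month 25 among 12 patients are 0.08–0.13, 0.19–0.33, 0.30–0.54 and 0.39–0.72 for the four accrual lengths. Progressions after v4.0 and before Month 25 are about 0.2, 0.7, 1.4 and 2.1–2.4 of 12.

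**6. Scale.** With 11 of 12 alive, the exact 95% interval is 62% to 99.8%, far wider than any bias in the second table.

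**The case against.** **The text is ambiguous.** The survival-status row, footnote 24 and 9.2.4 are current text. Section 7.2 says survival collection will continue, and does not itself name progression among the stopping events. This stands: a reader might infer that v4.0 plainly abolishes survival follow-up after progression, and the documents do not support that. They conflict. But 8.2.19 does make progression a trigger for the visit at which 7.2 stops, so a site following those two sections would stop. The marker tying footnote 24 to a table row cannot be read in the extracted text.

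**The shortening was deliberate.** The reasons for the amendment state: "A longer follow up was envisaged for efficacy assessment but has a limited value considering the reduced sample size". That explains the 25-month cap. It gives no reason to stop recording deaths at progression inside the cap.

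**Other routes to deaths exist.** The sponsor and investigator "may continue to use publicly available information to establish the survival status of patients who have withdrawn consent", but this is optional and does not cover a patient who progressed without withdrawing consent. Safety monitoring after progression and later SAE reporting are not vital-status follow-up.

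**A censoring rule may exist elsewhere.** A reader might infer that none exists at all. The documents show only that the supplied text has none; 10.1.2 assigns PK and biomarker analyses to a later SAP.

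**No estimator is promised.** Section 10.1 says only that OS will be summarised. If OS were merely listed patient by patient, there would be no biased curve, but deaths after the visit would still be absent.

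**Two further inferences fail.** The 6 to 12 points should not be read as the bias of the trial's OS: on the calendars above, with accrual complete before v4.0, no patient is wholly under v4.0. Nor does this point show that late AESI reporting is inadequate, since 9.2.5.1 provides for later reporting of AESIs.

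**Conclusion.** The point holds as a conflict in the current text with a limited statistical consequence. If 7.2 and 8.2.19 govern, OS for patients progressing after v4.0 is informatively censored at about progression and is pooled with OS collected under a longer rule.

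The bias is probably upward: about 0 to 2 percentage points at 24 months if accrual was complete before v4.0, and about 6 to 12 points at 25 months for any patient wholly under it. These sizes rest on uniform entry, constant hazards, assumed progression medians, complete survival follow-up before v4.0, and survival figures from groups that do not match this trial, which excludes anti-CD20-refractory patients. Actual accrual and the v4.0 approval date, which drive the result, are not stated.

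Severity is minor. OS is descriptive and untested in 6 to 12 patients. The primary safety endpoint and the dose recommendation, which rests on safety data, are unaffected.

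**What to change.** Choose one rule and make the text agree with it.

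1. **Keep OS.** In 7.2 and 8.2.19, record vital status to Month 25 regardless of progression or new therapy, for treated patients who have not withdrawn consent. Telephone contact is enough, as footnote 24 already describes. State the OS time origin and censoring rule in 10.1, including the rule for patients in survival follow-up when v4.0 was approved.
2. **Keep the current stop.** Delete OS from the synopsis, Table 3-1 and 10.1, or relabel it as survival censored at end of study or progression.

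With either choice, reconcile the survival-status row in Tables 1-1 and 1-2, footnote 24, and sections 4.5, 7.2, 8.2.19 and 9.2.4.

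The first option costs one to four six-monthly calls per progressed patient, in at most about 12 patients, within the existing 25-month cap. It partly reverses the amendment's shortening of follow-up. The second needs only a text change, and leaves an endpoint that claims less.

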## 7.3. Replacement policy

Patients will not be replaced in the study. However, if a patient is considered to be non-evaluable for dose evaluation, enrolment of a new patient to the current cohort will be considered if there is less than the required number of evaluable patients.

## 7.4. Lost to Follow-Up

A patient will be considered lost to follow-up if he/she repeatedly fails to return for scheduled visits and is unable to be contacted by the study site.

The following actions must be taken if a patient fails to return to the clinic for a required study visit:

- The site must attempt to contact the patient and reschedule the missed visit as soon as possible and counsel the patient on the importance of maintaining the assigned visit schedule and ascertain whether or not the patient wishes to and/or should continue in the study.
- Before a patient is deemed lost to follow-up, the Investigator or designee must make
  every effort to regain contact with the patient (where possible, 3 telephone calls and, if
  necessary, a certified letter to the patient's last known mailing address or local
  equivalent methods). These contact attempts should be documented in the patient's
  medical record.
- Should the patient continue to be unreachable, he/she will be considered to have withdrawn from the study with a primary reason of lost to follow-up.

Discontinuation of specific sites or termination of the study as a whole is discussed in Study Governance Considerations (Appendix 2).

## 8. Study Procedures

Safety and efficacy measurements obtained during the course of the study are summarised in the Schedule of activities (Section 1.2) and Section 4.

As highlighted in Section 8.2.2, safety assessments are to be performed before lilotomab infusion during Visit 3. Betalutin to be administered within 4 hours of lilotomab infusion.

Unless specified, blood samples at each visit to be taken before study drug administration. The urine pregnancy test at day 0 to be taken and negative results confirmed before lilotomab or Betalutin adminisitered.

12-lead ECG to be performed during visits described below and also at any other stage during the study if clinically indicated.

## 8.1. Screening Period

During the initial screening visit at the study site, the Investigator must inform each prospective study patient of the nature of the study, explain the potential risks, and obtain written informed consent from the patient prior to performing any study-related screening procedures. Once the informed consent document has been signed, the patient may undergo the screening procedures.

Pre-treatment period is defined from start of screening to the administration of the first RTX dose.

The tests and assessments outlined in Table 8-1 will be performed within 4 weeks prior to RTX infusion (pre-treatment period).

 Table 8-1
 Procedure and assessments at Screening Visit (Visit 1)

Assessment or Procedure	Explanation
Obtain Informed Consent	The patient must be fully informed about the study and sign the Informed consent form (ICF). The ICF needs to be signed before any treatment or study-related procedures are initiated.
Demographics	Date of birth, sex, ethnic origin, race should be recorded
Inclusion/exclusion criteria	See Section 5
Medical History	Record details of all previous or concomitant conditions or surgical procedures
Urinalysis	To check for urinary infection
Concomitant medication/therapy	If the patient is receiving any medication for conditions mentioned on the Medical History page, details need to be recorded on the Concomitant therapies record
Physical examination	Check and describe any significant abnormal physical examinations findings (heart, lung, abdomen, general, skin, oral cavity, chest and lymph nodes). Any abnormalities will be recorded on Medical History record
Height and weight	Record height and weight details
Vital signs	Systolic/diastolic blood pressure, heart rate, and body temperature

12-lead ECG	A copy of the medically reviewed ECG page will be
	signed, dated and interpreted before storing in the patient
	file
ECOG	ECOG performance status for study inclusion
Haematology	Including haemoglobin, platelet count, white blood cell
	count and differential (absolute count of neutrophils,
	lymphocytes, monocytes, eosinophils and basophils)
Serum biochemistry	Including sodium, potassium, calcium, magnesium,
	creatinine, urea, uric acid, alkaline phosphatase (ALP),
	aspartate transaminase (ASAT), alanine transaminase
	(ALAT), lactate dehydrogenase (LDH), gamma-
	glutamyltransferase (GGT), glucose, total bilirubin and
	albumin
Immunophenotyping	Define absolute cell counts for circulating T-cells, CD4 T-
	cells, CD8 T-cells, B-cells and NK cells, respectively
	defined as CD3+, CD3 + CD4 + , CD3 + CD8 + , CD19+ and
0 1.1	CD3 CD16 + CD56 + lymphocytes by flow cytometry
Coagulation	International normalised ratio (INR), partial
C ' 1	thromboplastin time (PTT)
Serum virology	HIV test, Hepatitis B test (HBsAg and anti-HBc),
Dungananan tart	Hepatitis C
Pregnancy test	For women of childbearing potential: serum beta human-
Immunaglabulin layala	chorionic gonadotropin (ß-HCG) pregnancy test Quantitative serum immunoglobulins (IgG, IgA and IgM)
Immunoglobulin levels HAMA screening	To screen for pre-existing human anti-mouse antibodies.
HAMA screening	A serum sample will be sent to a central laboratory
	(mandatory). Eligibility can be assessed using a local test
	such as the Milenia Quickline® HAMA test (optional)
Immunogenicity	Monitoring ADA response (RTX, lilotomab and Betalutin
	baseline)
Tumour tissue biopsy (if no available	Assessments to be performed:
archived FFPE block, a new surgical	Mandatory: CD20 and CD37 expression in
tumour tissue biopsy will be	tumour by immunohistochemistry
performed)	Mandatory: Calibration of the blood MRD test
	Optional: Gene expression analysis in tumour
	(DNA, RNA, proteins) to evaluate the
	relationship between anti-tumour activity and
	NHL-related genes.
	Note : If FFPE block not biobanked at Covance Central
	Laboratories (CCLS), preparation of the 5μM FFPE slides
	for the respective analyses only after Sponsor request
Optional: HLA haplotyping – (saliva	Human Major Histocompatibility Complex (MHC) class
sample direct or mouth swab, only if	I/II haplotyping
not possible to collect blood sample)	
Minimal Residual Disease	MRD monitoring to assess early treatment response and
(biopsy  and peripheral blood sample)	detect relapse (baseline)
Bone marrow, biopsy	To verify <25% tumour cells in bone marrow, biopsy
D. U. I	taken from a site not previously irradiated.
Radiology - FDG PET/CT	Using standard institutional guidelines. Patient needs to be
	fasting 6 hours prior to PET/CT examination. Information
	about FDG administration and standardised uptake value
	(SUV max ) will be recorded. The same camera should
	preferably be used throughout the study.

Radiology - CT scans with contrast or MRI	CT/MRI of neck, thorax, abdomen and pelvis. Information about contrast medium, target lesion location and measurements and non-measurable lesions will be	
	recorded. The same camera should preferably be used	
	throughout the study.	
Optional, only at Radium Hospital,	The following human biosamples will be collected:	
(Oslo, Norway): Exploration of the	
 
New tumour tissue biopsy (surgical)
 
	
anti-tumour T cell responses	Additional peripheral blood samples	
Adverse events	Any AEs occurring after informed consent has been	
	signed should be recorded	

<sup>1A sample of an archived tumour biopsy collected before treatment or a new tumour tissue biopsy collected at screening will be used to calibrate the blood MRD test (see tumour tissue biopsy).

